1.0 TRIAL SUMMARY

Abbreviated Title	Phase I Trial of MK-3475 and Concurrent Chemo/Radiation for the Elimination of Small cell lung cancer
Trial Phase	I
Clinical Indication	SCLC
Trial Type	Investigator initiated
Type of control	None
Route of administration	IV
Trial Blinding	NO
Treatment Groups	
Number of trial subjects	
Estimated duration of trial	
Duration of Participation	

2.0 TRIAL DESIGN

2.1 Trial Design: 3x3 dose escalation

[figure not shown]
2.2 Trial Diagram

- For Part A we will allow induction chemotherapy
- Primary Endpoint
 - Safety
- Secondary endpoint
 - Improvement in PFS compared to historical controls

[figure not shown]
Part A: Is only for patients with Limited Stage SCLC, we will allow induction chemotherapy. The total cycles of chemotherapy recommended will be 4, as such if a patient had two cycles of induction chemotherapy they would only get an additional two with MK-3475. PCI will be allowed based on the treating physician discretion and will be done after chemotherapy has been completed. PCI will delay the next dose of MK-3475 by one cycle and PCI should start approximately three weeks after MK-3475. MK-3475 can be resumed following the completion of PCI. LS-SCLC patients, who achieve systemic disease control during/after completion of 16 cycles of MK-3475, will be eligible to get additional 16 cycles of MK-3475, provided they did not exhibit severe (grade >3) MK-3475 related toxicity during therapy. Systemic disease control is defined as stable disease or partial response or complete response, based on irRC criteria.

Part A for LS-SCLC

* Eligible patients may receive additional 16 cycles.

Part B: Is only for patients with Extensive Stage SCLC who are receiving consolidation XRT after 1-6 cycles of chemotherapy. Patients needing PCI are encouraged to have it completed prior to enrollment in this trial. If PCI needs to be given on study, after thoracic XRT, then it should be done in a manner consistent with part A. PCI will delay the next dose of MK-3475 by one cycle and PCI should start approximately three weeks after MK-3475. MK-3475 can be resumed following the completion of PCI.) Patients needing XRT treatment to other sites outside the thorax will be allowed, but is encouraged to be done prior to starting the trial.

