4.2.3 Rationale for Endpoints

4.2.3.1 Efficacy Endpoints

Part A LS-SCLC: The primary endpoint is safety in order to establish the MTD of MK-3475 with concurrent chemo and radiation. The primary acute toxicity for chemo and radiation is esophagitis with a rate of $\geq 32\%$ ⁸. While the long term toxicity rate of grade 3 pneumonitis is around 13%⁹.

Part B ES-SCLC: The primary endpoint is safety in order to establish the MTD of MK-3475 with concurrent radiation. The primary acute toxicity for chemo and radiation is esophagitis with a rate of $\geq 32\%$ ⁸. While the long term toxicity rate of grade 3 pneumonitis is around 13%⁹.

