8.0 CHEMOTHERAPY

Part A LS-SCLC:

All patients will receive chemotherapy with either cisplatin and etoposide or carboplatin and etoposide. All patients should receive four cycles of chemotherapy, given over 3 weeks each, unless there is evidence of disease progression or patient intolerance. Cisplatin and etoposide is the preferred regimen; for patients unable to tolerate cisplatin in the opinion of the treating clinician, carboplatin/etoposide is an acceptable alternative.

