8.1 Drug Supply and Storage

Cisplatin, carboplatin, and etoposide are standard, commercially available drugs. Investigators will use commercially available supplies and will store drug as per the instructions provided in the package insert. This section does not apply to induction chemotherapy given prior to trial enrolment.

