9.1 Data Set Descriptions

This study will utilize a standard 3+3 design and dose de-escalation will proceed according to the following scheme. Three doses of MK-3475 (100 mg, 150 mg, 200 mg) will be given to 3 different groups of 3 patients. If the toxicity is greater than 1/3 in one group then the next lower dose will be used. This will establish the MTD, if present. If more than 1/3 of patients experience DLTs at the lowest dose (70 mg), it will be concluded that MK-3475 cannot be given safely with chemo/radiation. If one of three patients at any dose level experiences grade 3 or greater toxicity then another 3 patient will be accrued at the same dose level. If 1/6 patients has grade 3 or higher toxicity then escalation will proceed, if 2/6 has grade 3 or greater toxicity then this is declared the MTD. If 3/6 has grade 3 or greater then we will reduce the dose level.

Part A: Is only for patients with Limited stage SCLC, we will allow induction chemotherapy.

Part A for LS-SCLC

Part B: Is only for patients with Extensive stage SCLC who are receiving consolidation XRT after 1-6 cycles of chemotherapy.

[figure not shown]

Table 1: Dose De-escalation, For Part A and B

Dose Level	MK-3475 (dose during XRT)	Toxicity Assessment	New MK 3475 dose
+2	200mg Q 3 weeks	If over 1/3 grade 3 toxicity is seen	150mg Q 3 weeks
+1	150mg Q 3 weeks	If over 1/3 grade 3 toxicity is seen If 0/3 grade 3 toxicity is seen	100mg Q 3 weeks 200mg Q 3 weeks
0 (starting dose)	100mg Q 3 weeks	If over 1/3 grade 3 toxicity is seen If 0/3 grade 3 toxicity is seen	70mg Q 3 weeks 150mg Q3 weeks
-1	70mg Q 3 weeks	If over 1/3 grade 3 toxicity is seen	We will conclude MK-3475 cannot be safely given after Chemo/radiation

Once the MTD is determined for each study part we will accrue at this MTD until we reach a total of 40 patients for each study part. Should DLTs occur in more than 1/3 of patients enrolled into this expanded cohort, dosing at that level will be stopped. A review of all DLTs observed will be conducted, and the need to lower the dose will be based on the discussion and agreement between

the IRB and the Investigator. Once at dose level +2, if 0/3 toxicity is seen we will not close the study for new patient enrollment until the third patient has passed the DLT assessment period, because even if this third patient has a DLT was seen it would no change the dose for future patients as another 3 patients at the same dose level would be needed.

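### Part A: sections 2.2 and 8 can be read to give different chemotherapy counts after induction, and nothing readable keeps a patient with no chemotherapy left out of a dose-finding cohort

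*Combined protocol and SAP*

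**What the plan says.** On purpose, section 4.2.3.1 states for Part A: "The primary endpoint is safety in order to establish the MTD of MK-3475 with concurrent chemo and radiation". The opening of section 9.0 separates the two escalations by the same feature: Part A is with chemotherapy and Part B is without.

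On induction, section 2.2 says "Part A: Is only for patients with Limited Stage SCLC, we will allow induction chemotherapy", and section 9.1 repeats the permission. Section 2.2 then gives a total, "The total cycles of chemotherapy recommended will be 4", and a worked example, "if a patient had two cycles of induction chemotherapy they would only get an additional two with MK-3475".

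On protocol chemotherapy, section 8.0 says of Part A "All patients will receive chemotherapy with either cisplatin and etoposide or carboplatin and etoposide", followed by "All patients should receive four cycles of chemotherapy, given over 3 weeks each". The only exceptions it names are progression and intolerance. Section 8.1 adds "This section does not apply to induction chemotherapy given prior to trial enrolment". Sections 8.2.1 to 8.2.3 describe dosing in cycles 1 to 4 and cap each drug at four cycles. Sections 8.2.2 and 8.2.3 also call those on-study cycles an induction phase.

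**The concern.** There are two related defects.

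First, the plan does not say consistently whether induction counts toward the four cycles. Section 2.2 deducts it. Section 8.0 does not, and section 8.1 can be read as placing pre-enrolment induction outside the count altogether. Two investigators could treat the same patient differently and each cite the protocol.

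Second, the readable text sets no upper limit on Part A induction. A patient who arrives with all the recommended cycles already given could be enrolled, receive MK-3475 and radiation with no chemotherapy, and be counted when the Part A dose is judged. That patient gives no direct information on the combination whose MTD Part A is meant to establish, and the cohorts are small enough for one such patient to matter.

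**Working it through.** **Inputs.** Recommended total of 4 cycles, with induction counted (section 2.2). Four cycles for all Part A patients, no deduction stated (8.0). Cycle length 3 weeks, or 21 days (8.0). DLT window of 22 days from therapy initiation (9.1). Cohorts of 3, expanded to 6 (9.1).

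**Step 1: reproduce the plan's example.** Cycles left = 4 − induction cycles = 4 − 2 = 2, as section 2.2 states.

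**Step 2: apply both texts to other patients.** Under 2.2, cycles left = max(0, 4 − k) for k induction cycles. Under the literal reading of section 8, on-study cycles = 4 and the total = 4 + k.

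| Induction cycles k | Left under 2.2 | On study, literal section 8 | Total, literal section 8 |
|---|---|---|---|
| 0 | 4 | 4 | 4 |
| 1 | 3 | 4 | 5 |
| 2 | 2 | 4 | 6 |
| 3 | 1 | 4 | 7 |
| 4 | 0 | 4 | 8 |

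The two agree only at k = 0. At k = 2 the patient has 2 or 4 further cycles.

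**Step 3: who can have no chemotherapy left?** Only a patient with k ≥ 4, and only under section 2.2. The literal reading of section 8 never produces one.

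**Step 4: does anything exclude that patient?** The inclusion criteria (5.1.2) set no limit on prior cycles. Exclusion 4 in section 5.1.3 requires a two-week washout and recovery from earlier toxicity, and gives no number of cycles. By contrast, section 2.2 does give a range for Part B, 1 to 6 cycles. The evaluability sentence in section 9.1 concerns response, and the escalation and DLT rules there do not require that chemotherapy was given. Section 5.9, on subject replacement, has a heading but no readable text.

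**Step 5: how far does this reach the DLT count?** A 21-day cycle fits the 22-day window. Patients with k = 0 to 3 have at least one cycle left, which falls in the window if it starts with MK-3475. On that assumption only patients with k ≥ 4 are counted without chemotherapy.

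**Step 6: size.** One such patient is 1/3 (33%) of a first cohort or 1/6 (17%) of an expanded one. Turning that share into a change in the chance of escalating needs separate DLT rates with and without chemotherapy, and the documents do not give them. Section 4.2.3.1 prints the same esophagitis rate (at least 32%) and the same grade 3 pneumonitis rate (about 13%) for both parts.

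**The case against.** The strongest reply is that the plan, read as a whole, already settles both matters. Section 2.2 gives an explicit example. The four-cycle ceiling in section 8.2 is compatible with giving only two on study, section 8.0 can mean the same total of four, and the sentence in 8.1 sits under drug supply and may concern supply only. Sections 8.0 and 9.0 describe Part A as treated with chemotherapy, so a patient with none left does not fit the description. Several figures, including the one in section 2.2, are not shown and could carry a limit.

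Much of this stands. The difference between 2.2 and 8 is an ambiguity that can be read away, and the absence of a limit is established for the readable text only. But reading it away is left to each site, and the statement that all Part A patients receive chemotherapy cannot hold for a patient whose four cycles under 2.2 are used up. A description of the arm is also not a rule on who counts in a cohort.

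Three stronger readings are tempting, and the documents do not support them.

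- A reader might infer that the disagreement between 2.2 and 8 produces the patient without chemotherapy. It does not. That patient follows from section 2.2's total together with the missing limit.
- A reader might infer that such a patient is simply receiving Part B treatment. Sections 4.2.2 and 5.2.1.1 give Part A radiation twice daily and Part B radiation daily, and disease stage differs.
- A reader might infer a definite bias toward higher doses. Besides the missing rates, the lead DLT definition in 9.1 ties events to MK-3475 plus radiation, so the effect of absent chemotherapy on DLT counts is uncertain.

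**Conclusion.** The point holds in two parts. Sections 2.2 and 8.0 to 8.1, read literally, give different on-study chemotherapy for every patient with induction, for example 2 against 4 further cycles after two induction cycles, although section 8.2 also allows the 2.2 reading. Separately, under section 2.2 a patient with four or more induction cycles could enter Part A with no chemotherapy left and count toward the MTD of a combination that patient never received, contrary to section 8.0.

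The cohort problem is confined to that group. This rests on two conditions: that remaining chemotherapy starts with MK-3475, and that no limit appears in a figure not shown. The documents do not indicate how many such patients would enroll, so the effect on the selected dose cannot be quantified. It bears on the primary endpoint and should be settled in the text.

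**What to change.** Reconcile section 2.2 with sections 8.0 to 8.2 so that all state the same total and say whether pre-enrolment induction counts toward it. The sponsor decides which total applies. State whether the sentence in 8.1 covers drug supply only or the whole of section 8, and use the word induction for one thing throughout.

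In section 9.1, state that for the Part A MTD decision a patient counts in a dose-finding cohort only if protocol chemotherapy was started within the DLT window. Other treated patients stay in the safety tables. This is a counting rule for the analysis and leaves eligibility and treatment to the sponsor.

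The cost is protocol wording. The one downside is that a patient who does not count may need to be replaced, which could lengthen a cohort slightly.

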3.0 OBJECTIVE(S) & HYPOTHESIS(ES)

3.1 Primary Objective(s) & Hypothesis(es)

- (1) **Objective:** Safety of MK 3475 plus chemo/radiation for LS-SCLC and safety of MK 3475 plus radiation for ES-SCLC

Hypothesis: MK-3475 with chemoradiation for LS-SCLC and with radiation for ES-SCLC will demonstrate an acceptable toxicity profile comparable to previous trials

3.2 Secondary Objective(s) & Hypothesis(es)

- (1) **Objective:** MK-3475 will improve PFS compared to historical controls for LS-SCLC and ES-SCLC.

Hypothesis: The addition of MK3475 will provide T cell activation that will help improve both local and distant disease progression in SCLC.

3.3 Exploratory Objective

- (1) **Objective:**

MK-3475 will increase T cells and CD8 positive cells in non-irradiated tumors, compare before and after MK-3475.

Radiation will turn the tumor into a vaccine produce new antigens and stimulate T cells which can then circulate and increase T cell responses in the non-irradiated tumors

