5.5.1. Tumor tissues

Tumor tissue collected for diagnostic purposes within 3 months of study entry will be banked under an IRB-approved laboratory protocol and ten to thirty unstained slides or fresh frozen tumor from available tissues will be collected for baseline immune system testing before radiation treatment

Optional biopsy after the completion of radiation therapy:

A biopsy will be done (optional) within 7 days after completion of radiation therapy for immune response monitoring.

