5.5.2. Peripheral blood

Up to 150 mL of peripheral blood will be collected under an IRB-approved laboratory protocol (optional) for immune system monitoring described in this clinical protocol at the following time points:

- First collection: At baseline before the start of radiation therapy
- Second collection: within 7 days after completion of radiation therapy.

The treating physician or designee will have the option to cancel the laboratory protocol collection for patient safety without protocol deviation.

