6.0 TRIAL FLOW CHART

6.1 Study Flow Chart (All scheduled tests will be given a window of +/- 3 days)

Treatment Cycle/Title:	Main Study Screening	1	2	3	4	5	6-16 (additional 16 cycles, for eligible patients)	Post MK-3475 Follow up	Survival Follow-Up (>2yrs) ^a
Scheduling Window (Days):	-28 to -1		± 3	± 3	± 3	± 3	± 3	Every 12 weeks post discon	Every 12 weeks
Administrative Procedures									
Informed Consent	X								
Medical History	X								
Concomitant Medication Review	X	X	X	X	X	X	X	X ^a	
Trial Treatment Administration		X	X	X	X	X	X		
Survival Status								X ^{a, f}	X ^{a, f}
Clinical Procedures/Assessments									
Review Adverse Events		X	X	X	X	X	X		
Directed Physical Examination	X	X	X	X	X	X	X		
Vital Signs and Weight	X	X	X	X	X	X	X		
ECOG Performance Status	X								
Laboratory Procedures/Assessments: Analysis Performed by LOCAL Laboratory									
Pregnancy Test – Urine or Serum β-HCG	X ^d								
PT/INR and aPTT	X								
CBC with Differential	X	X ^f							
Comprehensive Serum Chemistry Panel (BMP)	X	X	X	X	X	X	X		
T3, FT4 and TSH ^b	X ^b		X ^b		X ^b		X ^b		
PFT's	X							X ^{c, f}	
Biopsy ^e		X ^g							

Treatment Cycle/Title:	Main Study Screening	1	2	3	4	5	6-16 (additional 16 cycles, for eligible patients)	Post MK-3475 Follow up	Survival Follow-Up (>2yrs) ^a
Scheduling Window (Days):	-28 to -1		± 3	± 3	± 3	± 3	± 3	Every 12 weeks post discon	Every 12 weeks
Blood Biomarker Testing ^e	X	X	X	X	X	X	X	X	
Efficacy Measurements									
Tumor Imaging (CT or PET scan) ^e	X				X		X ^f	X ^{e, f}	X ^{e, f}

- a. Can be done over the phone.
- b. Thyroid functions will be performed with every other MK-3475 cycle, if the first three test are WNL then it can be stopped.
- c. Optional biopsy after radiation treatment
- d. Within 2 weeks of study entry for women with child bearing potential.
- e. Imaging should be performed approximately every 12 weeks (± 4 weeks).
- f. standard of care
- g. Within 3 months of study entry

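### Section 3.3 credits MK-3475 with a T-cell rise in non-irradiated tumor, but tissue sampling is timed to radiation and names no lesion site, so the change mixes treatments and may include irradiated tissue

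*Combined protocol and SAP*

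**What the plan says.** The exploratory objective in section 3.3 reads: "MK-3475 will increase T cells and CD8 positive cells in non-irradiated tumors, compare before and after MK-3475". Its second sentence gives radiation a causal role too: radiation is expected to create antigens and prime T cells that then reach non-irradiated tumor.

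Section 5.5.1 supplies two tissue samples. The first is archival: "Tumor tissue collected for diagnostic purposes within 3 months of study entry will be banked under an IRB-approved laboratory protocol", and slides or frozen tissue "will be collected for baseline immune system testing before radiation treatment". The second is voluntary: "A biopsy will be done (optional) within 7 days after completion of radiation therapy for immune response monitoring". The flow chart in section 6.1 repeats this as "Optional biopsy after radiation treatment". Section 5.5 says that whatever tumor samples are available will be assessed, and leaves collection and analysis to a separate laboratory protocol that is not part of the document. Section 9.2.1 plans descriptive statistics for biomarker response.

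For blood, section 5.5.2 lists two optional collections. One is at baseline before radiation, and the other is given as "Second collection: within 7 days after completion of radiation therapy". The flow chart has a row headed "Blood Biomarker Testing" marked at screening, in every treatment-cycle column and at post-MK-3475 follow-up.

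**The concern.** The objective names one agent (MK-3475), one tissue (non-irradiated tumor) and one contrast (before against after MK-3475). The sampling text secures none of these fully. No lesion site is given at either time point. The timing anchor is radiation. Chemotherapy and radiation can both fall between the two samples.

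Section 4.2.1 builds the rationale on radiation priming a response that then acts systemically, and section 3.3 is the only tissue-level test of that idea. If in-field tissue is pooled with out-of-field tissue, a local radiation effect could be read as a distant immune effect. If the baseline predates chemotherapy, a chemotherapy effect could be read as an MK-3475 effect.

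**Working it through.** The plan states no sample size, power or expected number of pairs for this aim, so there is no figure to reproduce. The check sets the sections side by side, with date arithmetic and an illustrative yield.

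**1. Objective against sampling.**
- Tissue: 3.3 requires non-irradiated tumor; 5.5.1 and 6.1 name no site for either sample.
- Anchor: 3.3 uses MK-3475; 5.5.1 uses the start and end of radiation.
- Pairing: 3.3 is a before/after comparison. Nothing in 5.5.1 asks for the same lesion twice, and the second sample is optional.
- Analysis: 9.2.1 has no rule on which samples count toward 3.3. The in-field/out-field split in 7.1.2.5.1 and 9.2.4 is for imaging response only.

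**2. What lies between the samples.** Exclusion criterion 13 in 5.1.3 bars prior anti-PD-1 and anti-PD-L1 therapy, so diagnostic tissue taken before entry predates MK-3475. Table 1 in 9.1 describes the MK-3475 dose as the one given during radiation, so a biopsy after radiation should follow exposure. The trial diagrams are not shown, so the exact order of first dose and radiation cannot be checked. The same interval contains radiation in both parts. In Part A it contains concurrent chemotherapy, possibly preceded by induction (2.2, 4.2.2, 8.0). In Part B, patients enter after 1 to 6 chemotherapy cycles (2.2), which fall in the interval if the baseline was taken before them.

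**3. Is a pre-chemotherapy diagnostic sample inside the 3-month window?** Inputs: 3-week cycles with etoposide on days 1 to 3 (8.0 and 8.2.1, stated for Part A and assumed for Part B); a 2-week chemotherapy washout before study Day 1 (5.1.3); diagnosis no later than cycle 1 day 1; study entry taken as Day 1. For k cycles, the earliest gap from cycle 1 day 1 to study Day 1 is 21(k − 1) + 2 + 14 days.

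- k = 1: 16 days (2.3 weeks)
- k = 2: 37 days (5.3 weeks)
- k = 3: 58 days (8.3 weeks)
- k = 4: 79 days (11.3 weeks)
- k = 5: 100 days (14.3 weeks)
- k = 6: 121 days (17.3 weeks)

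Three months is about 13 weeks (91 days). After 1 to 4 cycles such a sample can fall inside the window, and it then predates chemotherapy. After 5 or 6 cycles it falls outside. If entry means the earliest screening day, 28 days before Day 1 (6.1), the last two gaps become 100 − 28 = 72 days (inside) and 121 − 28 = 93 days (just outside). So a baseline is available for some Part B patients and not assured for all.

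**4. What counts as non-irradiated.** Radiation to other sites is allowed on study (2.2, 4.2.2), and prior radiation needs no washout (5.1.3, criterion 4). The imaging definition in 7.1.2.5.1 classes a lesion as not treated if it was not irradiated under this protocol. A lesion outside the thoracic PTV may therefore still have been irradiated.

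**5. Illustrative yield.** Pairs per part = 40 × u × s, where u is uptake of the optional biopsy and s is the share of those patients with matched non-irradiated tissue. Neither is in the document; both are assumptions.
- u = 0.25, s = 0.1: 40 × 0.25 × 0.1 = 1
- u = 0.50, s = 0.3: 40 × 0.50 × 0.3 = 6
- u = 0.75, s = 0.5: 40 × 0.75 × 0.5 = 15

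Missing baselines would lower these further.

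**6. Blood.** Section 5.5.2 has two collections; the flow chart row marks every cycle. Either the schedules conflict or they describe different samples. The text does not say which.

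**The case against.** The strongest defence is that a usable contrast does exist. Section 5.5.1 names a baseline, the exclusion criteria keep it free of prior anti-PD-1 exposure, and the optional biopsy comes after radiation given with MK-3475. Site and handling may be fixed in the separate laboratory protocol. The aim is exploratory, the analysis is descriptive, and 3.3 itself mentions radiation.

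Much of that stands, and it rules out several stronger readings that a reader might infer:
- That there is no baseline before MK-3475. There is one; its weaknesses are that it is archival, not tied to a non-irradiated lesion and not assured for every patient.
- That the aim cannot be answered at all. An optional biopsy may happen to be out of field, and the laboratory protocol may specify the lesion.
- That Part A can contribute nothing. Few out-of-field lesions are likely, but this is inferred from limited stage; section 9.2.4 applies the out-field criteria to both parts.
- That the per-cycle blood row implies a very large total volume. The ceiling of 150 mL in 5.5.2 is not stated to be per draw, the flow chart row gives no volume, and section 7.1.2.6 places volumes in the Procedures Manual.

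The defence does not remove the attribution problem. A descriptive before/after change still cannot be assigned to MK-3475 when radiation, and in many patients chemotherapy, falls in the same interval. Nothing in the document keeps irradiated tissue out of the comparison.

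**Conclusion.** The wording of 3.3 goes further than the sampling can support. The before/after change reflects chemotherapy, radiation and MK-3475 together, and may include irradiated tissue. Non-irradiated pairs are possible but not ensured. Under the assumed ranges they number from 1 to 15 per part of 40, with Part A probably at the low end.

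This rests on the document alone. If the laboratory protocol fixes a non-irradiated site, the site point is settled by a cross-reference, but the mixing of treatments remains. The date check assumes 3-week cycles before entry in Part B. The flow chart's footnote letters may have been disturbed by text extraction, and nothing here depends on them.

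The primary safety objective is unaffected. This is a cheap improvement to an exploratory aim.

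**What to change.** - For each existing tissue sample, record the site, whether that site has been irradiated (in any field, before or during the study, not only the thoracic PTV), and the date relative to chemotherapy, radiation and the first MK-3475 dose.
- Count only non-irradiated samples toward 3.3. Report how many pairs there are in each part and how many come from the same lesion.
- Reword 3.3 so that changes are attributed to the combined treatment, not to MK-3475 alone.
- If the separate laboratory protocol already fixes the lesion to be sampled, cross-reference it in 5.5.1.
- Separately, reconcile the two blood collections in 5.5.2 with the per-cycle row in 6.1, or state that they are different samples.

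The cost is wording and a few recorded fields, with no extra biopsy. The downside is a narrower exploratory claim, possibly resting on very few pairs. Recording sites does not create pairs; it only makes clear which samples bear on the aim.
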